1 INTRODUCTION

1.1 Background

Rabies is an acute lethal viral disease transmitted from animals to humans. Rabies is present in more than 150 countries and territories and on every continent except Antarctica. All mammals are believed to be susceptible to infection with the rabies virus. In the US, multiple rabies virus variants are maintained in wild mammalian reservoir populations such as raccoons, skunks, foxes, and bats. Infected domestic and wild animals spread rabies to humans via bites or scratches (WHO 2017). Although the US has been declared free of canine rabies virus variant transmission, in developing countries, the primary route of transmission to humans is via the bite of a rabid dog (Manning et al. 2008). There are currently no known effective rabies antiviral drugs.

Once the clinical signs of rabies manifest, the mortality rate approaches 100%. Therefore, PEP against rabies infection is of critical importance. Rabies vaccination alone is used for pre-exposure prophylaxis (Immunization Practices Advisory Committee 1980). Studies on the development of rabies virus neutralizing activity through immunization indicate that on Day 7 post vaccination most individuals lack adequate rabies virus neutralizing activity while by Day 14 after immunization virtually all individuals vaccinated with a modern rabies vaccine have adequate rabies neutralizing activity (Grandien et al.1977, Vodopija et al.1988a)

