3.9 Study Efficacy Evaluations

3.9.1 Clinical Efficacy Evaluations

The absence of a confirmed or probable case of rabies in the per-protocol population is part of the composite endpoint. Subject will be periodically evaluated for the clinical signs and symptoms of human rabies. If these develop they will be referred for medical evaluation and laboratory or anatomic confirmation. All clinical rabies diagnostic tests may be performed locally at a qualified laboratory. All rabies cases will be reviewed by the DSMB.

Human Rabies Clinical Case Definition:

A person presenting with an acute neurological syndrome (encephalitis) dominated by forms of hyperactivity (furious rabies) or paralytic syndromes (dumb rabies) progressing towards coma and death, usually by respiratory failure, within 7-10 days after the first symptom if no intensive care is instituted.

A subject who is alive and not hospitalized is presumed not to have rabies. Contact with a non-hospitalized subject on any date is evidence that rabies has not occurred on that date. If a subject is discharged from hospital rabies has not occurred.

Case Classification Human Rabies

- Suspected: A case that is compatible with the clinical case definition
- Probable: A suspected case (above) plus history of contact with a suspected rabid animal.
- Confirmed: A suspected case that is laboratory-confirmed.

Rabies Laboratory Diagnosis Confirmation Criteria

One or more of the following:

- Rabies viral isolation from clinical specimens
- RVNA in the CSF
- Detection of rabies viral RNA by RT/PCR in clinical specimens, saliva,
- Detection of rabies by FAT on skin biopsy such as from neck (ante mortem).
- Detection of rabies by FAT preferably brain tissue (collected post mortem).

- Detection of rabies by FAT after inoculation of brain tissue, saliva or CSF in cell culture, or after intracerebral inoculation in mice or in suckling mice.
- Detection of viral nucleic acids by PCR on tissue collected before or after death in a clinical specimen (brain tissue or skin, cornea, urine, saliva or other).

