6.1.2 Confirmation of Rabies in Trial Participants

Any laboratory confirmed or clinically suspected case of rabies occurs in the blinded trial the administration of Study Drug will be paused for DSMB confirmation of rabies diagnosis and review. The DSMB must confirm rabies in a case of the per protocol population before

unblinding of that case is considered. If a confirmed case of rabies occurs in the per-protocol unblinded SYN023 treated group the DSMB will issue a written communication permanently stopping enrollment and Study Drug administration. A rabies case will not be reported as an adverse event since it is an element of the primary objective.

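### Protocol 3.9.1 lets hospital discharge rule out rabies with no check on survival or test results, and lets CSF RVNA alone upgrade a clinical case to confirmed

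*Protocol*

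**What the plan says.** Protocol Section 3.9.1 contains both the rules for excluding rabies and the rules for classifying it.

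- **Exclusion.** One sentence is a presumption: "A subject who is alive and not hospitalized is presumed not to have rabies". The next treats contact with a non-hospitalised subject as evidence for that date only. The third has neither limit: "If a subject is discharged from hospital rabies has not occurred".
- **Clinical definition.** An acute encephalitic or paralytic syndrome, "progressing towards coma and death, usually by respiratory failure, within 7-10 days after the first symptom if no intensive care is instituted".
- **Classification.** A suspected case fits the clinical definition. A probable case is a suspected case with contact with a suspected rabid animal. A confirmed case is a suspected case with laboratory confirmation.
- **Laboratory confirmation.** "One or more of the following" is enough, and the list includes "RVNA in the CSF" with no titre, no comparison with serum and no exception for treated subjects.

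Element 4 of the primary objective (Section 2.1) requires no probable or confirmed case in SYN023 recipients. Sections 1.6 and 7.3 explain that trial entry already supplies the animal exposure that makes a suspected case probable. Under Section 6.1.2, a confirmed case in the per-protocol SYN023 group leads to the DSMB "permanently stopping enrollment and Study Drug administration". SAP Section 8.1.1.4 repeats this rule for a confirmed case.

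**The concern.** The discharge sentence uses an administrative event as if it were an outcome. Rabies is excluded by survival beyond its expected course, by a negative work-up or by another diagnosis. Discharge guarantees none of these. Section 3.9.1 does not say which rule prevails when a discharged subject also meets the case classification. Since element 4 has no tolerance, the reading chosen for one subject can decide whether the primary objective is met.

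The CSF criterion raises a smaller question. Antibody in the CSF is offered as laboratory proof of infection in a trial where both arms receive anti-rabies antibody and a vaccine meant to raise more. As written, it cannot separate infection from study treatment, and the category it feeds is the one named in the permanent-stop rule.

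**Working it through.** **1. The plan's own figure for element 4.** Section 7.3 gives 0.63% with a 95% interval of 0 to 2% for one case in 160 per-protocol subjects.

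- Rate: 1/160 = 0.625%.
- Wald interval: 0.00625 ± 1.96 × √(0.00625 × 0.99375/160) = −0.60% to 1.85%. Truncated at 0, this rounds to the stated interval.
- The exact (Clopper-Pearson) interval is 0.02% to 3.43%.

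The figure is reproduced. It shows that the plan treats a single case as decisive.

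**2. Discharge sentence against the classification.**

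| Subject with the clinical syndrome | Classification rules | Discharge sentence |
|---|---|---|
| Discharged early or against advice, dies at home | Probable | Not rabies |
| Discharged to die at home | Probable | Not rabies |
| Discharged with a laboratory criterion met | Confirmed | Not rabies |

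Section 3.9.1 gives no order of precedence. Its own time course, "within 7-10 days after the first symptom if no intensive care is instituted", leaves days in which a subject with rabies is alive and can be discharged.

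**3. What hangs on one subject.** Inputs: a failure rate r of 0.1% to 0.01% and 184 SYN023 subjects in the NRG (Section 7.8.5), 160 of them per-protocol (Section 7.3). The chance of at least one true case is 1 − (1 − r)^n.

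- n = 184: 16.8% at 0.1%; 1.8% at 0.01%.
- n = 160: 14.8% at 0.1%; 1.6% at 0.01%.

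If the case rules recognise only a fraction s of true cases, the chance that element 4 fails is 1 − (1 − rs)^184. The values of s below are assumptions, because the documents give no rate of early, self- or terminal discharge.

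| s | r = 0.1% | r = 0.01% |
|---|---|---|
| 100% | 16.8% | 1.8% |
| 90% | 15.3% | 1.6% |
| 75% | 12.9% | 1.4% |
| 50% | 8.8% | 0.9% |

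**4. The CSF criterion traced through the rules.** Take a subject with the syndrome and RVNA in the CSF.

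- Without the CSF result: suspected, and probable because of the entry exposure. Element 4 already fails.
- With the CSF result: confirmed. Element 4 fails just the same.

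Keeping or removing the criterion changes element 4 by exactly zero. Only the category changes. Serum RVNA will be present in almost any such subject: in the historical data of Table 7.8.3-1, 73/73 SYN023 and 76/76 HRIG subjects were at or above 0.5 IU/mL on Day 42. The documents give no figure for passage of antibody into CSF, so the frequency of a false upgrade cannot be derived.

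**The case against.** **The discharge rule has a rationale.** Section 1.1 puts mortality close to 100% once signs appear, so a subject who leaves hospital alive is unlikely to have had rabies. A reader might infer that this fatality contradicts the rule. It does not; it is the reason for the rule. The gap is only that leaving hospital alive is not the same as surviving the illness.

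**The sentence can be read narrowly.** It follows one limited to a given date, and a careful adjudicator would not let it override a later positive sample. That is a sensible reading, but the text does not say so.

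**There are backstops.** Hospitalisation and death are serious adverse events (5.8), reported within 24 hours of site awareness (5.11) and collected to Day 365 (3.12.1). Any suspected or laboratory-confirmed case pauses dosing for DSMB review (6.1.2). A death stops enrolment unless the DSMB finds it unrelated (6.3). Contact is planned about every six weeks (2.4). These make a silently missed case less likely. They do not reconcile the sentences: the death rule asks about relation to SYN023, and the DSMB case review acts on cases already recognised as possible rabies.

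**CSF RVNA is not enough alone.** This stands. The clinical syndrome is also required, and the stop is not automatic: the DSMB, which should include an infectious disease or rabies expert (5.1.5), must first confirm the diagnosis. A reader might infer that any CSF antibody confirms rabies, or that a false CSF result could by itself fail the primary objective. The definitions support neither, since such a subject already counts as probable.

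**Conclusion.** The point holds in two parts of unequal weight.

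The main part is an internal inconsistency. The discharge sentence can declare a subject free of rabies whom the same section classifies as probable or confirmed. One such subject decides element 4. How often this would happen cannot be derived from the documents. The 16.8% to 1.8% is the chance of at least one true case at the sponsor's assumed rates, not the chance of missing one.

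The lesser part is that the CSF criterion is non-specific in treated subjects. Its effect is limited to a wrong upgrade from probable to confirmed. This matters under Section 6.1.2 and SAP 8.1.1.4, which name the confirmed category; Section 5.1.5.1 speaks of a case of rabies without naming one.

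Both are wording corrections worth making. With DSMB review behind the definitions, and no document-based rate for either error, they are not a critical flaw in the design.

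**What to change.** **Discharge.** Reconcile the sentences in Section 3.9.1 so that discharge rules out rabies only if no laboratory criterion was met and the subject is documented alive at a contact more than 10 days after discharge. Otherwise the DSMB adjudicates, including any out-of-hospital death without an established non-rabies cause. The 10 days come from the 7-10 day course in the case definition. For an illness that began before discharge, a contact more than 10 days after discharge is also more than 10 days after the first symptom.

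**CSF RVNA.** State that, in subjects given study drug or vaccine, CSF RVNA counts as confirmation only with a second listed criterion (virus isolation, antigen or nucleic acid). Otherwise the case stays probable and still counts against element 4. Carry the same definitions into SAP 8.1.1.4.

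**Cost.** Protocol and SAP wording, and one follow-up contact after a hospitalisation. A few subjects stay unresolved until that contact. If only the planned contacts are used, and these are at most six weeks apart, the wait is at most 10 + 42 = 52 days; a dedicated contact shortens it.

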3.9.2 Pharmacodynamic Efficacy Evaluations

The serum RVNA ≥ 0.5 IU/mL for the 365 day trial duration is the pharmacodynamic efficacy parameter. These specimens will be collected and forwarded to the study laboratory at the University of Kansas. These measurements will be used to calculate both superiority for Study Day 8 GMC RVNA and non-inferiority for Study Day 99 GMC RVNA and % population RVNA ≥ 0.5 IU/mL. A missing RVNA datapoint or RVNA data point less than 0.5 IU/mL preceded and followed by RVNA concentrations ≥ 0.5 IU/mL will be considered to be in the protective range.

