5.1.5.2 DSMB Evaluation of Safety and Pharmacodynamic Activity in the Initial Enrollment LRG

The sponsor will collect blinded RVNA results and adverse events through Study Day 29 from the subjects in the LRG initial enrollment group and provide this information to the DSMB. Permission to enroll the General Enrollment of the LRG may be granted if

- no protocol stopping rules are met (Section 6.3) and if
- no severe related adverse events other than local injection site manifestations are encountered due to SYN023 in the initial enrollment of the LRG
- the serum RVNA values are all in the protective range (≥ 0.5 IU/mL Section 3.9.2) on Study Days, 8 through 29 in the SYN023 recipients.

The DSMB will issue a written determination permitting enrollment of the general enrollment group of the LRG and inform the sponsor of this determination. It is acknowledged that some HRIG recipients may not have achieved ≥ 0.5 IU/mL RVNA by Study Day 8.

5.1.5.3 DSMB Review of Safety and Pharmacodynamic Activity in the Initial and General Enrollment LRG

The sponsor will collect blinded RVNA results and adverse events through Study Day 99 from all subjects in the LRG General and Initial enrollment groups and provide them to the DSMB. Permission to enroll the General Enrollment of the NRG may be granted at Study Day 183 if

- no protocol stopping rules are met (Section 6.3) and if
- no severe related adverse events other than local injection site manifestations are encountered due to SYN023 in the initial and general enrollment of the LRG
- The RVNA values are in the protective range in $\geq 75\%$ of SYN023 recipients on Study Day 99 (Section 3.9.2).

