3.4. Rabies Vaccine (RabAvert® or Rabipur®) Administration

Rabies Vaccine (RabAvert® or Rabipur®) must be administered in a different area from the study drug infiltration to reduce interference. The 1 mL dose of the chicken fibroblast rabies vaccine should be administered in deltoid muscle. If not possible, then vaccination may be administered

in the vastus lateralis (thigh) or rectus femoris (thigh). The rabies vaccine should be administered as soon as possible after dose constitution. Rabies vaccination should be administered within 75 minutes after study drug.

4. General Statistical Considerations

As it is unlikely that there is any clinical difference between the 4 and 5 dose regimens, summaries will be grouped by study group (LRG and NRG) regardless the difference in dosing schedules. In each summary where applicable, subjects will be grouped by treatment (actual study drug received). The two treatment groups for the study are SYN023 and HRIG.

Continuous data will be described using descriptive statistics (i.e. n , mean, standard deviation (SD), median, minimum, and maximum). Categorical data will be described using the subject count and percentage in each category. For the summary statistics of all numerical variables, unless otherwise specified, minimum and maximum will be displayed to the same level of precision as reported. Mean and median will be displayed to one level of precision greater than the data collected. SD/standard error (SE) will be displayed to two levels of precision greater than the data collected. P-values will be rounded to three decimal places. If a p-value is less than 0.001 it will be reported as “<0.001.” If a p-value is greater than 0.999 it will be reported as “>0.999.” Data will be displayed in all listings sorted by treatment group (actual study drug received).

Subjects will be identified in the listings by the subject identification number concatenated with the site number.

When count data is presented, the percentage will be suppressed when the count is zero to draw attention to the non-zero counts. Where applicable, a row denoted “Missing” will be included in count tabulations to account for dropouts and missing values. The denominator for all percentages will be the number of subjects in that treatment within the analysis set of interest, unless otherwise specified.

Unless otherwise specified,

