- baseline will be defined as the last non-missing assessment prior to the first dose date (and time, if available on Study Day 1).
- Change from baseline is defined as: post-baseline value – baseline value.

The Study Day will be calculated as follows:

- If the assessment date occurs on or after the date of the first dose of study drug:
Study Day = assessment date – first dose date + 1.
- If the date of interest occurs before the date of the first dose of study drug:
Study Day = assessment date – first dose date
- There is no Study Day 0.

Missing data will not be imputed except for incomplete or partial dates of adverse events (AEs) and concomitant medications. Imputation rules for such will be described in the corresponding sections.

By timepoint summaries will be based on case report form (CRF) visits. For efficacy analyses, unscheduled results will not be considered but only be listed in by-subject listings. For safety analyses, unscheduled results will not be presented in by-timepoint summaries. However, it will be considered for overall post-treatment maximum or minimum values when reporting safety abnormalities.

All analyses will be conducted using SAS Version 9.4 or higher. If not pre-specified, statistical tests will be two-sided and interpreted at a 5% significance level.

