7.2.2. Treatment Compliance and Modifications

Compliance will be summarized for rabies vaccinations. Treatment compliance is defined as the ratio of total number of vaccinations to the planned number of vaccinations, in terms of percentage. Treatment compliance will be summarized descriptively for both the As-treated and the Per-protocol Populations.

8. Efficacy Analysis

The primary and secondary efficacy endpoints may be performed on the As-treated and the Per-protocol Populations. The Per-protocol analyses will be considered primary; the As-treated analyses will be considered supportive. The denominator for all percentages will be the number of subjects in that treatment within the analysis set of interest, unless otherwise specified.

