8.1.1.3. Non-inferiority on RVNA Response Rate

The third element is immune response to the rabies vaccine on Study Day 99 measured by the noninferiority percent of the study population RVNA ≥ 0.5 IU/mL SYN023 vs HRIG. This approach assesses the noninferiority of the percent of subjects who have a serum RVNA concentration that is generally recognized as protective, the more important measure of vaccine compatibility.

The alternative hypothesis (H_a) is that the response rate in SYN023 vaccine (r_{SYN023}) is non-inferior to HRIG (r_{HRIG}) by a 20% margin (0.8 in terms of a ratio). Given that the statistics can be defined as the rate ratio $\emptyset = \frac{r_{SYN023}}{r_{HRIG}}$, the alternative hypothesis can be written as:

$$H_a: \emptyset = \frac{r_{SYN023}}{r_{HRIG}} > 0.8$$

and the null hypothesis as:

$$H_0: \emptyset = \frac{r_{SYN023}}{r_{HRIG}} \leq 0.8.$$

As the rate ratio \emptyset and the rate difference $\Delta = r_{SYN023} - r_{HRIG}$ are interchangeable with log transformation, it is equivalent to test on the test statistic Δ with Pearson's chi-square test or, in case of small sample sizes (responders in either group is less than 5 subjects), Fisher's exact test. This can be achieved by using SAS procedure FREQ (use the option *riskdiff* and additional option *Newcombe* with the *tables* statement). In the summary table, by-treatment risk rates with corresponding SDs, risk ratio and the asymptotic CI for the risk ratio based on the Wilson score method will be back transformed and displayed. In case of small sample sizes, an exact CI based on the Clopper-Pearson method will be presented instead. The null hypothesis will be rejected at a significance level of 2.5% ($\alpha = 0.025$) if the lower bound of the two-sided 95% CI for the risk ratio is greater than the non-inferiority bound 0.8.

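### Protocol 3.9.2 can count a missing or measured sub-0.5 IU/mL Day 99 RVNA value as a response, while the SAP has no such rule

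*Protocol*

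**What the plan says.** Primary element 3 compares the arms on the percentage of subjects with RVNA ≥ 0.5 IU/mL on Study Day 99, against a ratio bound of 0.8.

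**Protocol.** Section 3.9.2 says the RVNA measurements feed that percentage. Its next sentence says "A missing RVNA datapoint or RVNA data point less than 0.5 IU/mL preceded and followed by RVNA concentrations" at or above 0.5 IU/mL "will be considered to be in the protective range". Two DSMB advancement criteria cite Section 3.9.2 for the protective range. Section 5.1.5.2 requires that "the serum RVNA values are all in the protective range" on Study Days 8 to 29 in SYN023 recipients. Section 5.1.5.3 requires this of at least 75% of SYN023 recipients on Study Day 99.

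**SAP.** Section 8.1.1.3 describes the element as the "noninferiority percent of the study population RVNA ≥ 0.5 IU/mL SYN023 vs HRIG" and says it assesses "the percent of subjects who have a serum RVNA concentration that is generally recognized as protective". It has no bracketing rule. Section 4 says: "Missing data will not be imputed except for incomplete or partial dates of adverse events (AEs) and concomitant medications". Section 8 says: "The denominator for all percentages will be the number of subjects in that treatment within the analysis set of interest, unless otherwise specified". Section 11.1, on RVNA, leaves missing concentrations out of the calculation. Section 14 declares no change to the planned analysis.

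**The concern.** Counting a measured Day 99 value below 0.5 IU/mL as a success is not missing-data handling. It replaces the stated endpoint (the level on Day 99) with something closer to the level around Day 99. The rule works in one direction: it adds responders and never removes them. When the same share of failures is bridged in each arm, the arm with more failures gains more, so a real deficit shrinks.

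For a missing Day 99 value that is bracketed, the documents give three answers:

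- responder (Protocol 3.9.2)
- in effect non-responder (SAP 4 and 8, where the subject stays in the denominator)
- excluded (SAP 11.1)

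A primary element should not have its responder rule open when the data are unblinded. Bracketing also supplies no concentration, so one subject could be a responder in element 3 and missing from the Day 99 GMC in element 2.

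**Working it through.** **1. The plan's own figure.** Protocol 7.8.3 gives totals of 32 (bound 0.8) and 72 (bound 0.9), with 100% response in both arms and one-sided alpha 0.025. In the Miettinen–Nurminen score test for a ratio R, when everyone responds the restricted estimates are 1 for HRIG and R for SYN023. This gives z² = (1 − R)(2n − 1)/(2R), with n per arm, which must reach 1.96² = 3.84.

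- R = 0.8: (2n − 1)/8 ≥ 3.84, so n = 16 and the total is 32.
- R = 0.9: (2n − 1)/18 ≥ 3.84, so n = 36 and the total is 72.

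Both figures reproduce, and neither depends on the bracketing rule.

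**2. Historical rates.** Table 7.8.3-1, Day 112: SYN023 70/73 = 95.9%, HRIG 75/76 = 98.7%, ratio 0.972. With 160 per arm (the per-protocol 320 of Protocol 2.3), power against 0.8 exceeds 99.9% without any bridging.

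**3. Type I error at the bound.** Inputs: HRIG 98.7%, SYN023 0.8 × 98.7% = 79.0%, 160 per arm. Let f be the share of non-responders bridged, the same in both arms (an assumption). The counted rate becomes p + f(1 − p). Rejection probabilities come from exact binomial enumeration of the score test in step 1, which stands in for the interval described in SAP 8.1.1.3.

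| f | SYN023 counted | HRIG counted | Ratio | Type I error |
|---|---|---|---|---|
| 0 | 79.0% | 98.7% | 0.80 | 2.1% |
| 5% | 80.0% | 98.8% | 0.81 | 4.1% |
| 10% | 81.1% | 98.8% | 0.82 | 7.6% |
| 25% | 84.2% | 99.0% | 0.85 | 32.6% |

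**4. How large f might be for measured lows.** Table 7.8.2-1 gives SYN023 GMCs of 2.33 (Day 84) and 1.43 (Day 112), a factor of 1.43/2.33 = 0.61 over 28 days. Their confidence intervals imply log SDs of 1.12 and 1.16. On a falling curve, a Day 99 low followed by a Day 127 value ≥ 0.5 comes mainly from visit-to-visit noise. A simulated log-linear decline, bracketed by Days 71 and 127, gave:

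| Assumed within-subject log SD | SYN023 lows bracketed | Gain in SYN023 rate |
|---|---|---|
| 0.1 | 0% | 0 points |
| 0.2 | 0.8% | 0.1 points |
| 0.35 | 7.1% | 0.9 points |
| 0.5 | 16.5% | 2.2 points |

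The model puts 13% of SYN023 subjects below 0.5 at Day 99. The historical study had none at Day 84 and 3/73 = 4.1% at Day 112, so these gains are probably at the upper end. Allowing non-adjacent visits would widen the rule.

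**5. Missing Day 99 values.** Let p = 95.9% among those observed and m = the fraction missing, all bracketed (assumed).

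| Reading | Formula | m = 5% | m = 10% |
|---|---|---|---|
| Protocol 3.9.2 | p(1 − m) + m | 96.1% | 96.3% |
| SAP 11.1, excluded | p | 95.9% | 95.9% |
| SAP 4 and 8, full denominator | p(1 − m) | 91.1% | 86.3% |

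**6. DSMB gates.**

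- *Initial gate, Day 8.* A measured SYN023 value below 0.5 between adequate Day 4 and Day 15 values would count as protective.
- *Initial gate, Day 15.* The citation of 3.9.2 conflicts with Section 3.9.3, which requires ≥ 0.5 IU/mL in all subjects without bracketing, and with Section 2.2.2.
- *Initial gate, Day 29.* The data package ends that day, so there is no following value.
- *NRG gate.* The package ends at Day 99, so bracketing works only if later data are supplied. The decision falls at Day 183, so that is possible. In that case, with 45 SYN023 recipients (34 needed) and an assumed true rate of 70%, the chance of passing is 26% with no bridging, 34% at f = 5% and 42% at f = 10%.

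**The case against.** The strongest reply is that little would change in practice. SYN023 response was 100% at Day 84 and 95.9% at Day 112 in the historical study, far above what a 0.8 bound needs, and falling titres make a recovery after Day 99 unlikely. That stands. The larger type I error figures need SYN023 near 79% and rest on assumed bridging shares.

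The sentence could also be read as serving the opening parameter of 3.9.2, protection over the 365 days. However, the Day 99 percentage is named between that parameter and the rule. Protocol 7.9.2 allows modifications to be placed in the SAP, so the SAP could be taken to govern, but SAP 14 declares none.

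Four stronger inferences are not supported:

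- *Repeat prophylaxis after a second bite lifts the later value.* A second bite requiring PEP and prohibited treatment are both per-protocol exclusions (Protocol 3.2.6, SAP 5.2), so this can reach only the as-treated analysis.
- *The rule would erase the Day 112 failures (3/73 and 1/76).* Table 7.8.3-1 has no later visit, so nothing shows they would be bracketed.
- *The documents differ by 5 to 10 points.* That holds only under the full-denominator reading. Under SAP 11.1 the gap at 5% missing is 0.2 points.
- *Early SYN023 lows would be hidden.* The Day 8 GMC, the AUEC and the listings still use the actual values. Historical SYN023 response was 98.7% at Day 3 and 100% at Days 7 to 28. SAP Table 4.1-1 also places the initial LRG under Protocol 2.0, so that gate has probably passed (an inference).

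**Conclusion.** The concern holds as an unreconciled responder definition for a primary element. Protocol 3.9.2, as written, lets a measured Day 99 failure count as a success. The SAP does not, and it offers two further treatments of a missing value. The direction is certain, since responder rates can only rise. The expected size is small: no change to the element 3 conclusion at historical rates, and about 0 to 2 points for measured lows under the assumed noise.

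It matters if SYN023 lies near the bound, where bridging 10% of non-responders takes type I error from 2.1% to 7.6%, or if many Day 99 samples are missing. All bridging shares, noise levels and missing fractions are assumptions. The effect on the gates is limited to a Day 8 gap, a Day 15 contradiction, and an NRG gate route that needs data from after Day 99.

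**What to change.** 1. In Protocol 3.9.2 and SAP 8.1.1.3, state that a measured RVNA value below 0.5 IU/mL is a non-response at that visit, for element 3 and for the per-visit percentages.
2. State one pre-specified handling of a missing Day 99 value in both documents. Observed cases as primary with missing counted as non-response as sensitivity is one option. The reverse is equally defensible. Align SAP 4, 8 and 11.1 with the choice.
3. If bracketing is kept, limit it to missing values between adjacent visits and label it a sensitivity analysis.
4. Reconcile Protocol 3.9.2, 3.9.3, 2.2.2, 5.1.5.2 and 5.1.5.3 on what counts as the protective range at the DSMB gates. Which rule the gates use is for the sponsor and the DSMB to settle.

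The cost is about a sentence in each document for the responder definition, plus the gate reconciliation. The reported responder rate may be slightly lower. The stated sample sizes of 32 and 72 do not change.
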